6.5. Dose Modifications

Dose modification guidance for AEs that have been previously observed in participants receiving parsaclisib or are potential class-effect AEs are provided (see Table 7). The starting dose and dose reduction levels of parsaclisib are provided (see Table 8). Individual decisions regarding dose interruption and reduction should be made using clinical judgment and in consultation with the sponsor's medical monitor, taking into account relatedness of the AE to the study treatment and the participant's underlying condition. Adverse events that have a clear alternative explanation or transient (≤ 72 hours) abnormal laboratory values without associated clinically significant signs or symptoms may be exempt from dose-reduction guidelines.

Table 7: Guidelines for Interruption and Restarting of Study Drug

ADVERSE EVENT	ACTION TAKEN
Chemistry	

 • AST and/or ALT is Grade 3 ($> 5.0 \times$ ULN). 
Note: In participants with liver metastasis-related elevations at baseline, contact sponsor to discuss clinical management and possible dose reductions.
	
Step 1: Interrupt parsaclisib and monitor weekly until the toxicity has resolved to \leq Grade 1.
 
Step 2: Restart parsaclisib at next lower dose with medical monitor approval. Monitor as clinically indicated.

Table 7: Guidelines for Interruption and Restarting of Study Drug (Continued)

ADVERSE EVENT	ACTION TAKEN
Hematology	

 • Grade 3 ANC ($< 1.0 \times 10^9/L$). • Platelet count is Grade 2 (50 to $< 75 \times 10^9/L$) for participants who enrolled with platelets $> 100 \times 10^9/L$. • Platelet count is Grade 3 ($< 50 \times 10^9/L$) for participants who enrolled with platelets $\leq 100 \times 10^9/L$. 	
Step 1: Interrupt pascalisib up to 14 days until the toxicity has resolved to \leq Grade 1 or pretherapy baseline. For Grade 3 ANC, monitor at least weekly.
 
Step 2: Restart pascalisib at same dose; monitor as clinically indicated.

 • Grade 4 ANC ($< 0.5 \times 10^9/L$). • Grade 3 or Grade 4 febrile neutropenia. • Platelet count is Grade 4 ($< 25 \times 10^9/L$). 	
Step 1: Interrupt pascalisib up to 14 days until the toxicity has resolved \leq Grade 2. (Monitor ANC at least weekly.)
 
Step 2: Restart pascalisib at same dose. Monitor as clinically indicated. If recurs, start at next lower dose.

Other toxicities	

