
 • Skin toxicity (eg, rash, pruritus, etc, unless otherwise specified) (Grade 2-3). 	
Step 1: Interrupt piasaalisib until the toxicity has resolved to ≤ Grade 1.
 
Step 2: Restart piasaalisib at same dose. If assessed as related to piasaalisib, restart at next lower dose.
						

 • Exfoliative dermatitis (Grade 1). 	
Step 1: Interrupt piasaalisib until the toxicity has resolved.
 
Step 2: Restart piasaalisib at next lower dose. Monitor as clinically indicated.
						

 • Exfoliative dermatitis (≥ Grade 2). 	Permanently discontinue piasaalisib.						

 • Intestinal perforation (any grade). 	Permanently discontinue piasaalisib.						

 • Pneumocystis jiroveci pneumonia infection. 	Interrupt piasaalisib. Permanently discontinue piasaalisib if Pneumocystis jiroveci pneumonia infection is confirmed.						

Table 7: Guidelines for Interruption and Restarting of Study Drug (Continued)

ADVERSE EVENT	ACTION TAKEN
Other toxicities (continued)	

 • CMV infection. 	Participants with CMV viremia without associated clinical signs of CMV infection should be carefully monitored. Consider interrupting parsaclisib for participants with CMV viremia and clinical signs of infection until the infection has resolved. Restart parsaclisib reduced by 1 dose level if approved by the medical monitor.

 • Varicella zoster infection. 	Interrupt parsaclisib. Restart parsaclisib only by approval of the medical monitor.

 • Any Grade 1 or Grade 2 toxicity unless otherwise specified. 	Continue parsaclisib and treat the toxicity; monitor as clinically indicated.

 • Any Grade 3 toxicity, if clinically significant and not manageable by supportive care unless otherwise specified. 	
Step 1: Interrupt parsaclisib up to 14 days until the toxicity has resolved to \leq Grade 1.
 
Step 2: Restart parsaclisib at same dose. If assessed as related to parsaclisib, restart at next lower dose. If interrupted for > 14 days, contact the medical monitor for approval to restart parsaclisib. Monitor as clinically indicated.

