### **9.3.3. Potential Hy's Law Events**

Participants with elevated ALT or AST  $> 3 \times$  ULN range and alkaline phosphatase  $< 2 \times$  ULN range accompanied by total bilirubin  $> 2 \times$  ULN range at the same visit will be listed.

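### At ALT/AST above 3 and up to 5 × ULN, with bilirubin above 2 × ULN but below Grade 3 and ALP below 2 × ULN, Table 7 continues parsaclisib, although the SAP calls this a potential Hy's law event

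*Protocol*

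**What the plan says.** **SAP 9.3.3** is headed as covering potential Hy's law events. It selects participants with ALT or AST above 3 × ULN, ALP below 2 × ULN and total bilirubin above 2 × ULN. The only consequence is a listing: "ULN range at the same visit will be listed".

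**Protocol 6.5, Table 7** has one liver row, under Chemistry. It is triggered when "AST and/or ALT is Grade 3", which the table sets at above 5.0 × ULN, whatever the bilirubin. The drug is interrupted with weekly monitoring until Grade 1 or lower, and then: "Restart parsaclisib at next lower dose with medical monitor approval". A note covers abnormal baselines: "In participants with liver metastasis-related elevations at baseline, contact sponsor to discuss clinical management and possible dose reductions".

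An event without its own row goes to a general row:

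- **Grade 1 or 2:** "Continue parsaclisib and treat the toxicity; monitor as clinically indicated".
- **Grade 3:** interruption applies to "Any Grade 3 toxicity, if clinically significant and not manageable by supportive care unless otherwise specified". Restart is at the same dose, or one level lower if the event is related. After more than 14 days off drug, the site must "contact the medical monitor for approval to restart parsaclisib".
- **Other Grade 4:** discontinue, unless the sponsor approves an exception.

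No Table 7 row names bilirubin or the combination. Nor does Protocol 9.5.1 (adverse events of special interest, AESIs), which has ALT and AST only from 5 × ULN, or SAP 9.3.4 (laboratory events of special interest).

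**The concern.** The SAP picks out a pattern that grading one analyte at a time can miss. The site, however, doses from Table 7, which looks at single analytes. Within one band, the combination that the SAP flags therefore receives a weaker instruction than an isolated transaminase rise.

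What is at stake is participant safety: continued dosing, and no fixed interval for repeat liver tests, during what may be early drug-induced liver injury. Liver events are within the table's stated purpose, which is "Dose modification guidance for AEs that have been previously observed in participants receiving parsaclisib or are potential class-effect AEs". The table also already departs from the general Grade 1 or 2 row where grade alone is thought to understate risk: Grade 1 pneumonitis, Grade 1 exfoliative dermatitis and Grade 2 skin toxicity all call for interruption.

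**Working it through.** The plan states no figure to reproduce. The check applies the Table 7 rows to the SAP 9.3.3 thresholds, with ALP below 2 × ULN throughout.

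| Case | ALT or AST (× ULN) | Total bilirubin | Meets SAP 9.3.3? | Table 7 row | Instruction |
|---|---|---|---|---|---|
| A | 5.1 | normal | no | Chemistry (5.1 > 5.0) | interrupt, weekly checks, restart one level lower with approval |
| B | 4 | 2.5 × ULN, taken as below Grade 3 | yes (4 > 3; 2.5 > 2) | Grade 1 or 2 (4 is not > 5.0) | continue |
| C | 4 | > 2 × ULN and Grade 3 | yes | general Grade 3 | interrupt only if the row's condition is met; approval needed only after more than 14 days |
| D | 4 | > 2 × ULN and Grade 4 | yes | other Grade 4 | discontinue |
| E | above 5.0 | > 2 × ULN, below Grade 4 | yes | Chemistry | as case A |

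B is looser than A. C is also looser, but conditionally so. D is stricter than A, and E is already covered.

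**Bilirubin band.** SAP 9.3.1 grades laboratory values by CTCAE v5.0, but the documents do not print the bilirubin limits. Call the lower limit of Grade 3 L × ULN. Case B then covers bilirubin from just above 2 × ULN up to L × ULN. If L were 2 or less, B would be empty and C would apply.

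**Dose difference (Table 8).** In the first 8 weeks, case A restarts at 10 mg QD instead of 20 mg. From Day 57 it restarts at 1 mg QD instead of 2.5 mg. In case B the dose stays at 20 mg or 2.5 mg. The footnote to Table 8 puts everyone on 2.5 mg at Day 57 whatever the earlier dose (diarrhea/colitis modifications excepted). Week 4 is Day 29, so a 20 versus 10 mg difference that starts at that draw lasts about 57 − 29 = 28 days, less the interruption.

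**Time to the next scheduled chemistry draw (Protocol Table 4).** Weeks 2 and 6 are hematology only. Between Weeks 4 and 48 the gap is 28 ± (3 + 3) = 22 to 34 days. Between later 12-weekly visits it is 84 ± (7 + 7) = 70 to 98 days. Case A requires weekly checks, while case B sets no interval.

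**Does the trigger mark a change on study?** The entry limits in Protocol 5.1 are ALT/AST 2.5 × ULN (5 × with liver involvement) and bilirubin 1.5 × ULN (Gilbert's syndrome exempt). With neither condition, both values must have risen past the entry limit: 3.0 − 2.5 = 0.5 and 2.0 − 1.5 = 0.5, so each by more than 0.5 × ULN. Only a participant with both conditions could meet the combination at entry.

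**The case against.** The best counter-argument is that Table 7 is guidance. Protocol 6.5 leaves individual decisions to clinical judgment in consultation with the medical monitor, and 6.5.4 wants safety concerns raised with the sponsor at once. Section 7.1.1 provides for discontinuation for a related event that is against the participant's interest, and 9.2 allows an important medical event to be reported as serious. Sections 8.3.1, 9.1 and 9.3 ask for a diagnosis rather than separate findings, so an investigator could record liver injury as one event and grade it 3. All of this stands and narrows the gap. It does not close it, because each route depends on someone recognising the pattern and none gives a liver threshold.

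The comparator is also softer than it looks. Section 6.5 says that abnormal laboratory values lasting no more than 72 hours, without clinically significant signs or symptoms, may be exempt from dose reduction. That stands too. It tempers case A without making case B strict.

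Finally, nothing in the documents reports such a case with parsaclisib, and the class toxicities named in Protocol 2.3 do not include liver injury. This limits the urgency. Table 7 nevertheless has a liver row, under a scope of observed or potential class effects.

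**Conclusion.** The point holds for a defined band: ALT or AST above 3 and up to 5 × ULN, bilirubin above 2 × ULN but below Grade 3, and ALP below 2 × ULN. There Table 7 says continue, which is less strict than its rule for an isolated transaminase above 5.0 × ULN. With a Grade 3 bilirubin, a weaker, conditional version remains. What is missing is a numeric prompt, not oversight. The frequency is unknown.

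Three stronger readings are tempting, and the documents do not support them:

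- **Table 7 continues drug in every potential Hy's law event.** It does not; see cases C, D and E.
- **SAP 9.3.3 is itself defective because it needs all values at one visit.** It is a reporting rule. Shift tables and chemistry listings still show bilirubin that rises later, so only a derived flag would be lost.
- **The efficacy result is at risk.** Protocol 8.2.1 says imaging is not to wait for a treatment interruption, and the objective response analysis does not use this rule.

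The conclusion rests on two assumptions: that Grade 3 bilirubin begins above 2 × ULN, and that the combination deserves at least the care given to an isolated ALT/AST above 5.0 × ULN. The second is a clinical judgment. The SAP's label points that way, but the documents do not state it.

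**What to change.** Add a row to Table 7, Chemistry, at least as strict as the existing ALT/AST row:

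> ALT or AST > 3 × ULN with total bilirubin > 2 × ULN and ALP < 2 × ULN at the same visit: interrupt parsaclisib and contact the medical monitor. Check ALT, AST, ALP and bilirubin weekly until Grade 1 or lower, or baseline. Restart only with medical monitor approval, at the next lower dose. The Grade 1 or 2 row does not apply; any stricter row (eg, Grade 4) still does. For participants with liver involvement or Gilbert's syndrome at baseline, contact the sponsor.

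Table 8 has no level below 1 mg QD, so for a participant already at that dose the medical monitor would have to decide, as under the existing row.

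Add the same combination to the AESI list in Protocol 9.5.1. That entry brings follow-up to resolution or stabilization; the Table 7 row is what changes dosing. SAP 9.3.3 can stay as it is.

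**Cost.** A protocol amendment with health authority and IRB/IEC approval (Protocol 11.1), and a few interruptions that will prove unrelated to the drug. All four analytes are already in Protocol Table 9, so no new analyte or scheduled visit is needed beyond the weekly repeats for affected participants. Amendment 4 brings the study to an earlier close, so the benefit is limited to participants still on drug.

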6.5.1. Supportive Care Guidelines for Diarrhea/Colitis

Participants should be informed to immediately report to the investigator any event of diarrhea. Treatment with piasalisib may be interrupted or modified according to the guidelines in [Table 7](#) to allow for resolution of diarrhea/colitis.

Participants should receive appropriate supportive care measures as deemed necessary by the investigator. For any Grade ≥ 1 diarrhea, participants should be advised to drink liberal quantities of clear fluids. If sufficient oral fluid intake is not feasible, fluid and electrolytes should be substituted via IV infusion. Participants should try to eat 5 to 6 small meals per day; low-fat, high-protein foods; and cooked instead of raw vegetables. Participants may supplement their diet with bananas, rice, applesauce, and toast to reduce the number of bowel movements and may also try crackers, gelatin, noodles, or oatmeal. Participants should avoid fried, fatty, greasy, or spicy foods; milk, milk products, and acidic drinks; high-fiber foods and foods that cause gas; and alcohol, caffeine, and herbal supplements ([Coutré et al 2015](#)).

For each occurrence, attempts should be made to rule out other causes, such as metastatic disease or bacterial or viral infection (including CMV), which might require additional supportive care.

It may be necessary to perform conditional procedures such as colonoscopy with biopsy as part of evaluation of the event. Note that several courses of steroid tapering may be necessary as symptoms may worsen when the steroid dose is decreased.

Participants should be carefully monitored for signs and symptoms of enterocolitis (such as diarrhea, abdominal pain or cramping, blood or mucus in stool, with or without fever) and of bowel perforation (such as peritoneal signs and ileus).

6.5.2. Supportive Care Guidelines for Neutropenia and Thrombocytopenia

Neutropenia and thrombocytopenia appear to be PI3K δ class-effect toxicities. Investigators should ensure that participants understand the need to seek medical care when they have conditions that could become life-threatening in the presence of cytopenias (eg, neutropenic fever or bleeding with low platelets). Participants should be instructed to report immediately any signs of infection, unexpected bleeding, or sudden, extremely painful headaches.

6.5.3. Definition for Immune-Related Adverse Events

Adverse events of a potential immunologic etiology, or irAEs, may be defined as an AE consistent with an immune phenomenon associated with study treatment exposure after all other etiologies have been eliminated. Immune-related AEs may be expected based on previous experience with piasalisib and other PI3K inhibitors. Special attention should be paid to AEs that may be suggestive of potential irAEs. Based on emerging data from the ongoing Study INCB 50465-101, most irAEs occur after the first 9 weeks of study treatment administration. However, an irAE could occur at any time. Suspected irAEs should be discussed with the medical monitor when possible.

Participants should receive appropriate supportive care measures as deemed necessary by the treating investigator. Suggested supportive care measures for the management of drug-related AEs with potential immunologic etiology are outlined in [Table 7](#) and Section 6.5.1. For each AE, attempts should be made to rule out other causes, including but not limited to metastatic disease or bacterial or viral infection, which might require specific supportive care.

6.5.4. Criteria and Procedures for Dose Interruptions

Safety concerns should be discussed with the sponsor immediately upon occurrence or awareness to determine if the participant should continue or discontinue study treatment.

Treatment with piasclisib may be delayed up to 14 days to allow for resolution of toxicity. Participants may resume treatment if no medical condition or other circumstance exists that, in the opinion of the investigator, would make the participant unsuitable for further participation in the study. The treating investigator should contact the sponsor to discuss the case of any participant whose treatment has been delayed for more than 14 days before restarting treatment with piasclisib.

6.6. Concomitant Medications and Procedures

All concomitant medications and treatments must be recorded in the eCRF. Any prior medication received up to 30 days before the date of study treatment administration (Day 1) will be recorded in the eCRF. Any addition, deletion, or change in the dose of these medications will also be recorded. Concomitant treatments and/or procedures that are required to manage a participant's medical condition during the study will also be recorded in the eCRF. The medical monitor should be contacted if there are any questions regarding concomitant or prior therapy.

6.6.1. *Pneumocystis Jirovecii* Prophylaxis

All participants are required to receive a standard PJP prophylaxis regimen determined by the investigator. Examples of standard PJP prophylaxis therapies for this population include trimethoprim-sulfamethoxazole, atovaquone, diaphenylsulfone with or without pyrimethamine, and pentamidine (diaphenylsulfone and pentamidine are not approved for PJP prophylaxis in Japan) ([NCCN 2020](#)). Due to reports of cross-sensitivity between sulfonamides and dapsone, all participants who have a known or suspected allergy to sulfonamides must receive atovaquone for PJP prophylaxis. Trimethoprim-sulfamethoxazole or atovaquone can be used for PJP prophylaxis in this study. Prophylaxis should be given while participants are receiving study treatment and should continue for 2 to 6 months after the last dose of study treatment.

The prophylactic agents will be obtained from commercial supplies and will be reimbursed by the sponsor. Investigators are responsible for ensuring that participants receive commercially available supplies of the selected prophylactic agents as required per Protocol. The sponsor may provide prophylactic agents where required by applicable law or regulation or under other limited circumstances when a participant may not otherwise have access to these therapies. The contents of the label will be in accordance with all applicable regulatory requirements. Further details are available in the Pharmacy Manual.

6.6.2. Restricted Medications and Procedures

- Use of systemic corticosteroid doses ≤ 10 mg/day prednisone (or equivalent) is permitted but discouraged from the screening visit through EOT.
- Short courses of systemic corticosteroid doses > 10 mg/day prednisolone or equivalent are permitted only in the case of severe or life-threatening complications that cannot be controlled with other drugs, but are otherwise discouraged from the screening visit through EOT.
- Use of weak or moderate inducers or inhibitors of CYP3A4 (see [Appendix B](#) and consult your local pharmacist) is discouraged, and investigators should seek other options where possible.
- For participants receiving pascalisib, P-glycoprotein substrates of clinical relevance should be used with caution (ie, aliskiren, ambrisentan, colchicine, dabigatran etexilate, digoxin, everolimus, fexofenadine, imatinib, lapatinib, maraviroc, nilotinib, posaconazole, ranolazine, saxagliptin, sirolimus, sitagliptin, talinolol, tolvaptan, topotecan).
- Localized radiotherapy will be permitted if administered as treatment for pain or impending compression fractures and with prior approval of the medical monitor.

6.6.3. Prohibited Medications and Procedures

- Use of potent inducers and inhibitors of CYP3A4 are prohibited (see [Appendix B](#) and consult your local pharmacist). Based on the low overall bioavailability of topical ketoconazole, there are no restrictions on topical ketoconazole.
- Apart from the study treatments, the use of any anticancer medications as described (see Section 5.2) through the 30-day follow-up is prohibited.
- Exposure to a live vaccine within 30 days of study treatment through 3 months after the last dose of INCB050465.

6.7. Treatment After the End of the Study

At the end of the study as defined in Section 8.9, participants who have completed at least 12 months of study participation (starting from the first dose of study treatment), who remain on active study treatment, and who have no evidence of PD may continue treatment. Any remaining participants may continue to receive study treatment and be seen by the investigator per usual standard of care for this participant population. In addition, the investigator will be expected to monitor for and report any SAEs, ECIs, and pregnancies, as detailed in Section 9. The participants is considered on study until such time that they meet any of the discontinuation criteria and written notification is given to the sponsor.

7. DISCONTINUATION OF STUDY TREATMENT AND PARTICIPANT DISCONTINUATION/WITHDRAWAL

7.1. Discontinuation of Study Treatment

The decision to discontinue study treatment will not constitute study completion. In the event that study treatment is discontinued, the treatment period will be considered complete, and follow-up periods will begin.

7.1.1. Reasons for Discontinuation

Participants **must** be discontinued from study treatment for the following reasons:

- The participant has died.
- The participant has experienced an unacceptable toxicity defined as follows:
 - Occurrence of an AE that is related to study treatment that, in the judgment of the investigator or the sponsor's medical monitor, compromises the participant's ability to continue study-specific procedures or is considered to not be in the participant's best interest.
 - Persistent AE requiring a delay of therapy for more than 2 weeks (14 days) unless a greater delay has been approved by the sponsor.
- The participant is unable to tolerate study treatment.
- The participant has an objective radiographic tumor response of PD/PMD.
- Further participation would be injurious to the participant's health or well-being, in the investigator's medical judgment.
- The participant becomes pregnant.
- Informed consent is withdrawn. *Note:* Consent withdrawn means that the participant can no longer be followed. Participants may choose to discontinue study treatment and remain in the study to be followed for disease progression and survival per the schedule of assessments.
- The participant is considered lost-to-follow-up when they repeatedly fail to return for scheduled visits and is unable to be contacted by the study site (eg, after 3 telephone calls and/or a certified letter or local equivalent).
- The study is terminated by the sponsor.
- The study is terminated by the local health authority, IRB, or IEC.

Participants **may** be discontinued from study treatment in the following situation:

- If a participant is noncompliant with study procedures or study treatment administration in the investigator's opinion, then the sponsor should be consulted for instruction on handling the participant.

